# TRIAL SUMMARY

Trial Title	Acetazolamide as a chloride sparing Diuretic in patients Admitted with Heart Failure: a pilot study					
Internal ref. no. (or short title)	ADA-HF					
Clinical Phase	Phase II					
Trial Design	Open label, randomised, controlled, pilot and exploratory study.					
Trial Participants	Patients admitted to Castle Hill Hospital with venous congestion due to heart failure who are deemed to require a continuous intravenous infusion (IVI) of furosemide at (10mg/hr) – standard of care for severe venous congestion.					
Planned Sample Size	40 (maximum recruitment of 50)					
Treatment duration	4 days					
Follow up duration	180 days					
Planned Trial Period	30 weeks					
Primary Objective	1) Difference in net fluid loss daily and over a 4 day period					
	2) Difference in serum chloride between baseline and day 4					
Secondary Objective	Differences between the two groups during the 4 day treatment period in:					
	1) daily urine output					
	2) daily weight					
	3) serum electrolyte levels (sodium, bicarbonate and potassium)					
	4) incidence of electrolyte abnormalities; hyponatraemia (<135 mmol/L), hypochloraemia (<96 mmol/L), hypokalaemia (<3.5 mmol/L), high (>30 mmol/L) or low (<22 mmol/L) serum bicarbonate.					
	5) change in renal function measured by serum creatinine (µmol/L) and estimated glomerular filtration rate (eGFR) (ml/min/1.72m2)					
	6) change in urinary electrolyte levels after 48 and 96 hours of treatment; sodium, chloride, potassium.					
	7) clinical assessment of congestion					
	8) ultrasound measures of congestion period; inferior vena cava (IVC) diameter.					
	9) change in breathlessness score using the Likert scale.					
	10) time to clinical euvolaemia and end of intravenous therapy					
	11) length of stay					
	12) rate of adverse events related to acetazolamide – treatment arm only					
	13) rate of adverse events					

Hull University Teaching Hospitals

	NHS T					
	14) Tate of recruitment to study					
	15) time taken to screen & recruit					
	16) rate of drop-out after randomisation – cause specific					
	17) Cause specific hospitalisation or mortality after 30 days and 180 days follow up.					
Investigational Medicinal Product(s)	Acetazolamide					
Formulation, Dose, Route of Administration	Tablet. 250mg twice daily. Oral.					
	Inclusion					
Main inclusion/exclusion	
 
Aged ≥18 of any gender
 
					
criteria	2) Able to give informed written consent to participate in the trial					

# Hull University Teaching Hospitals

	5) Concurrently taking high dose aspirin (>500mg / day)
	methotrexate, lithium, or sodium valproate – risk of drug interactions with ACZ
	6) Concurrently taking Sando-K®, oral sodium bicarbonate, or other sodium tablets – confounding electrolyte analysis
	7) Concurrently taking oral steroids – confounding diuretic analysis
	8) Peripheral oedema due to heart failure that has been triggered by an underlying illness such as severe anaemia (haemoglobin < 8 g/DL) or concurrent severe infection (requiring intravenous antibiotics).
	9) SBP <80 mmHg at randomisation
	8) Serum sodium (severe hyponatraemia) <130 mmol/L at randomisation
	9) Serum potassium (hypokalaemia) <3.5 mmol/L at randomisation
	10) Serum chloride (severe hyperchloraemia) >110 mmol/L at randomisation
	11) Severe renal dysfunction with an eGFR (estimate glomerular filtration rate) result of $\leq$ 30 ml/min calculated by the Cockcroft-Gault formula
	12) Pregnant or breast feeding, or intends to become pregnant whilst taking part in the trial
Investigations performed	As part of routine practice: Admission and daily blood tests including serum electrolytes, renal function and NTproBNP; chest x-ray; echocardiogram; daily weight; daily urine output; fluid balance (volume in minus volume out).
	As part of study: daily weight; daily urine output; daily fluid balance; daily urine for electrolytes on days 2 and 4; daily clinical assessment of congestion as detailed above; daily ultrasound assessment of congestion as detailed above; daily patient-rated symptom severity using Likert scale; daily diet sheet to record daily salt and fluid intake.
Biological samples to be taken from patients	Urine and serum.
Planned trial sites	Ward 39 at Hull Royal Infirmary, [name] and wards 26 & 28 and Cardiac Monitoring Unit at Castle Hill Hospital, [name]

# LIST OF ABBREVIATIONS

Define all unusual or 'technical' terms related to the trial. Add or delete as appropriate to your trial. Maintain alphabetical order for ease of reference.

ACZ	Acetazolamide
AE	Adverse Event
AHF	Acute heart failure
AR	Adverse Reaction
CA	Competent Authority
CI	Chief Investigator
CRF	Case Report Form
СТА	Clinical Trial Authorisation
CTIMP	Clinical Trial of Investigational Medicinal Product
DSUR	Development Safety Update Report
EC	European Commission
EMEA	European Medicines Agency
EU	European Union
EUCTD	European Clinical Trials Directive
EudraCT	European Clinical Trials Database
GCP	Good Clinical Practice
HF	Heart failure
IB	Investigator Brochure
ICF	Informed Consent Form
ICH	International Conference on Harmonisation of technical requirements for registration of pharmaceuticals for human use.
IMP	Investigational Medicinal Product
IMPD	Investigational Medicinal Product Dossier
ISF	Investigator Site File
ISRCTN	International Standard Randomised Controlled Trials Number
MA	Marketing Authorisation
MHRA	Medicines and Healthcare products Regulatory Agency
MS	Member State
NHS R&D	National Health Service Research & Development
NIMP	Non-Investigational Medicinal Product
NTproBNP	N-terminal pro-B-type natriuretic peptide
PI	Principal Investigator
PIS	Participant Information Sheet

EudraCT: 2022-001566-34

Quality Assurance
Quality Control
Randomised Control Trial
Research Ethics Committee
Serious Adverse Event
Serious Adverse Reaction
Standard Operating Procedure
Summary of Product Characteristics
Site Specific Information
Suspected Unexpected Serious Adverse Reaction
Trial Management Group
Trial Steering Committee
Trial Master File
Inferior Viene Cours

# **KEY WORDS:**

Acetazolamide, Heart Failure, Chloride, Hypochloraemia, Diuretics, In-patient

# 1 BACKGROUND

The cornerstone of treatment for congestion in patients with heart failure is loop diuretics such as furosemide or bumetanide, but failure to respond or worsening despite increasing dose of diuretic - diuretic resistance - is common. Current guidelines recommend the addition of a thiazide (or thiazide-like) diuretic (e.g. bendroflumethiazide or metolazone) when a patient has become 'resistant' to loop diuretics. However, only a few small studies have tested the effects of thiazide and thiazide-like diuretics in patients with heart failure with inconsistent results.

Loop and thiazide diuretics prevent sodium reabsorption in the loop of Henle and distal tubule but the majority of renal sodium reabsorption (~70%) occurs in the proximal tubule. Reabsorption of sodium in the proximal tubule depends predominantly on the sodium-hydrogen (Na+/H+) antiporter. Carbonic anhydrase catalyses the interconversion between carbon dioxide and water on the one hand, and hydrogen (H+) and bicarbonate ions on the other. Increased intracellular H+ concentration promotes sodium reabsorption in the proximal tubule by increased activity of Na+/H+ antiporters. Thus carbonic anhydrase inhibitors (such as acetazolamide) reduce sodium reabsorption in the proximal tubule and act as a diuretics.

Early studies of acetazolamide in the 1950-60s in patients with heart failure, before the advent of loop diuretics, found that high dose acetazolamide (>1000mg per day) used alone was less effective than standard of care at the time (intramuscular mercurial diuretics). However, more recent studies have found that acetazolamide at doses between 250-750mg daily may have both natriuretic and diuretic effects when used in combination with loop diuretics or spironolactone, and may have a greater diuretic effect than thiazide diuretics.

The recent ADVOR study of 500mg intravenous acetazolamide or placebo alongside intravenous furosemide found that acetazolamide was associated with greater diuresis and recovery from decompensated heart failure. However, the median dose of furosemide given in the study was 120mg per day, which is less than half the mean dose used in the high-dose arm of the DOSE trial, a fraction of what was permitted in the pharmacological treatment arm of the CARESS-HF trial, and half of what might be considered standard of care in the UK. Furthermore, only a third of patients had oedema above the knee. Given the low doses of loop diuretic used and the fact two thirds had only moderate oedema, the majority of patients in the study may not have needed hospitalization at all. How acetazolamide effects diuresis in patients given larger doses of intravenous loop diuretic in patients with severe congestion, the majority of patients admitted to hospital with heart failure. remains unanswered by the ADVOR trial.

An additional benefit of acetazolamide may be increased renal chloride reabsorption and thus increased serum levels during diuresis. Hypochloraemia is an important marker of a poor prognosis in patients with HF but whether it causes a poor prognosis is unclear. There are mechanisms by which hypochloraemia may drive worsening heart failure and diuretic resistance. Prevention or correction of hypochloraemia may be a worthwhile therapeutic goal in patients with HF. The effect of ACZ on chloride homeostasis in patients with HF is untested in a prospective randomised controlled trial (RCT): whether acetazolamide may act as a "chloride-sparing diuretic" is unknown.

# 2 RATIONALE

Symptoms of venous congestion due to heart failure is the leading cause of admission to hospital for patients aged  $\geq$ 65 and causes or complicates 5% of all hospital admissions in the UK. In the last 5 years, hospitalisation rates have increased by a third, more so than for any other medical condition. The median length of stay in hospital for patients with heart failure is 9 days and tends to be longer if the patient is under the care of a heart failure specialist, reflecting the time taken to adequately treat the venous congestion – "decongestion".

High dose diuretic prescriptions and long hospital stays are both associated with greater risk of adverse outcome in patients with heart failure compared to patients requiring lower doses or shorter periods of admission. Furthermore, failure to respond or worsening symptoms despite increasing dose of diuretic - diuretic resistance - is common.

One possible reason for the association between high dose diuretic and adverse outcome is diureticinduced electrolyte abnormalities: hyponatraemia and hypokalaemia are well recognised complications of diuretic treatment, and adverse prognostic markers in admitted with heart failure. Hypochloraemia (<96 mmol/L) is common in patients with HF and is associated with high dose diuretic treatment and a higher risk of mortality, independent of prognostic markers such as amino-terminal pro-B-type natriuretic peptide (NTproBNP) *and* other electrolytes including sodium and potassium.

While hyponatraemia and hypokalaemia have been therapeutic targets in some recent trials, data on pharmacological manipulation of chloride levels is scarce. Amongst patients admitted with heart failure, those with hypochloraemia that resolves by the time of discharge appear to have a similar post-discharge prognosis as patients with normal chloride levels throughout admission. Conversely, incident hypochloraemia is associated with an increased risk of adverse outcome post-discharge. Some small trials of acetazolamide have reported increased chloride levels alongside increased diuresis in patients admitted with heart failure. However, doses of loop diuretic and other medications in these studies was variable and data on daily changes to serum and urinary electrolytes lacking.

Whether acetazolamide has a significant diuretic effect in patients also taking standard treatment in the UK (240mg / 24 hours IV furosemide infusion) is unknown. Furthermore, how it affects renal chloride excretion and whether it can correct hypochloraemia or prevent incident hypochloraemia due to high dose loop diuretic is unknown.

There is a pressing need to clarify whether or not acetazolamide can increase diuresis and / or favourably affect renal chloride excretion. Our pilot and exploratory study will provide data to estimate the effect of acetazolamide on diuresis and serum chloride concentrations during treatment with IVI of furosemide at 10mg/hr (standard of care in the UK for patients admitted with severe venous congestion).

It will also provide data on the possible tolerability of acetazolamide and recruitment rate to a study of acetazolamide in patients hospitalised with heart failure in the UK.

Should the data suggest a favourable effect on either diuresis and / or chloride homeostasis during diuresis then the results of study will be used to design a large multi-centre randomised placebo controlled trial of acetazolamide combined with high dose loop diuretics to prevent or correct hypochloraemia during in-patient diuresis.

# 2.1 Dosing and study duration

Acetazolamide is currently licenced to treat glaucoma and epilepsy, and is used in the prophylaxis of high altitude pulmonary oedema. The British National Formulary recommends doses between 250-1000mg per day in divided doses. We chose a dose of 250mg twice daily based on dosing in previous contemporary trials which appeared to show some diuretic effect with acetazolamide, and the relatively low rate of side-effects reported in much earlier studies with doses <500mg per day.

The oral route was chosen as other adjunctive diuretics such as bendroflumethiazide or metolozone are also given orally. A study period of 4 days was chosen to represent approximately half the median duration of in-patient stay in the UK over which time we would expect to see some biochemical and clinical improvements in response to standard of care.

# 2.2 Assessment and management of risk

The British National Formulary lists the common or very common side effects of acetazolamide to be: ataxia, depression, diarrhoea, dizziness, fatigue, flushing, irritability, headache, loss of appetite, nausea, vomiting, taste disturbance, parasthesiae, reduced libido, polyuria, and thirst. Notable uncommon side effects include: metabolic acidosis, electrolyte disturbances, blood disorders, skin rashes and symptoms consistent with renal calculi.

The early studies suggested that side effects such as drowsiness and paraesthesia are seen in 14-38% of patients with heart failure at doses >1000mg per day, although side-effects were less common at doses ≤500mg per day (5-10%). Modern day studies did not report any adverse events but it is not explicitly stated that this is due to the medication being well tolerated.

We judge the above side effects to be of low clinical risk to the patient however it is possible a patient experiencing any one of the those side effects after starting acetazolamide may wish to end their participation. This, in itself, would be a useful endpoint. One of the many unknowns about acetazolamide in contemporaneous studies is the tolerability used either in isolation or in conjunction with high dose loop diuretic.

There are potential risks to the patient from the combination of acetazolamide and high-dose loop diuretic treatment, however we are unable to estimate their expected frequency: 1) increased risk of hyponatraemia – as both medications increase urinary sodium excretion; 2) increased risk of symptomatic hypotension due to increased intravascular volume loss and 3) increased risk of renal dysfunction. Daily assessment of urine and serum electrolytes and the patient will detect any changes that might be associated with increased risk to the patient and these will be discussed with the patient regarding continuation. Again, this would be a useful endpoint in itself regarding tolerability of the combination of diuretics. Furthermore, worsening electrolyte abnormalities, symptomatic hypotension and worsening renal function would be expected in the standard care arm also.

Ultimately we would expect all treatment related adverse events to resolve upon withdrawal of the study treatment should the patient wish to do so or if the risk to the patient was felt too great to allow their continuation in the study.

Aside from the IMP, we anticipate no increased risk to either the patient or study staff by their participation in the study. All data will be recorded on paper CRFs and stored in a locked filing cabinet in an office with a locked door on NHS property accessible only via swipe-card. It will then be transferred to a password-protected Excel spreadsheet on a password protected NHS server behind an NHS firewall.

# 3 OBJECTIVES AND OUTCOME MEASURES/ENDPOINTS

# 3.1 Research Question

What are the effects of acetazolamide 250mg BD by mouth (PO) in conjunction with 240mg/24 hours furosemide IVI on diuresis and chloride homeostasis compared to 240mg/24 hours IV furosemide infusion alone (standard of care).

# 3.2 Primary objective

# Primary hypothesis

The addition of 250mg acetazolamide orally twice-daily to 240mg / 24hr IV furosemide infusion willNHS Trust increase diuresis while also reducing the amount by which serum chloride concentrations fall during diuresis in a patient admitted to hospital for venous congestion due to heart failure compared to furosemide infusion alone.

# Null hypothesis

The addition of 250mg acetazolamide orally twice-daily to 240mg / 24hr IV furosemide infusion will have no effect on diuresis or serum chloride concentrations in a patient admitted to hospital for venous congestion due to heart failure compared to furosemide infusion alone

# 3.3 Secondary objectives

# Secondary hypothesis

Acetazolamide is well tolerated in patients admitted to hospital with heart failure and neither the time taken to screen and recruit patients and collect data, or the rate of recruitment will be prohibitive to a larger study of acetazolamide in the same patient population.

# 3.4 **Primary endpoint/outcome**

Difference in mean net fluid loss daily and over a 4 day period

• Total volume intake in millilitres (mL) – total volume passed as urine in mL

Difference in serum chloride concentrations between day 1 and day 4

• Serum chloride day 4 – serum chloride day 1

# 3.5 Secondary endpoints/outcomes

All secondary endpoints are exploratory designed to inform future research.

Differences between the two groups during the 4 day treatment period in:

1) daily weight

2) serum electrolyte levels (sodium, bicarbonate and potassium)

3) incidence of electrolyte abnormalities; hyponatraemia (<135 mmol/L), hypochloraemia (<96 mmol/L), hypokalaemia (<3.5 mmol/L), high (>30 mmol/L) or low (<22 mmol/L) serum bicarbonate.

4) change in renal function measured by serum creatinine (µmol/L) and estimated glomerular filtration rate (eGFR) (ml/min/1.72m2)

5) change in urinary electrolyte levels after 48 and 96 hours of treatment; sodium, chloride, potassium.

- 6) clinical assessment of congestion
- 7) ultrasound measures of congestion period; inferior vena cava (IVC) diameter
- 8) change in breathlessness score using the Likert scale.
- 9) time to clinical euvolaemia and end of intravenous therapy

10) length of stay

11) rate of adverse reactions, serious adverse reactions and suspected unexpected serious adverse reactions – treatment arm

- 12) rate of adverse events and serious adverse events both arms
- 13) rate of recruitment to study
- 14) time taken to screen & recruit
- 15) rate of drop-out after randomisation cause specific
- 16) Cause specific hospitalisation or mortality after 30 days and 180 days follow up.

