#### Exclusion criteria

1) Unable to give informed written consent

2) Allergy or contraindication to carbonic anhydrase inhibitors

3) Patient thought to be at end-of-life

4) Concurrently taking thiazide (or thiazide-like) diuretic or sodium-glucose linked transporter-2 inhibitor, high dose aspirin (>500mg / day), methotrexate, lithium, or sodium valproate, oral steroids Sando-K®, oral sodium bicarbonate, or other sodium tablets

5) Severe anaemia (haemoglobin <8 g/DL); or severe infection (investigator opinion).

6) SBP <80 mmHg at randomisation

7) Serum sodium (severe hyponatraemia) <130 mmol/L at randomisation

8) Serum potassium (hypokalaemia) <3.5 mmol/L at randomisation

9) Serum chloride (severe hyperchloraemia) >110 mmol/L at randomisation

10) Severe renal dysfunction with an eGFR (estimate glomerular filtration rate) result of  $\leq$ 20 ml/min calculated by the Cockcroft-Gault formula

12) Pregnant or breast feeding, or intends to become pregnant whilst taking part in the trial

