#### 7.9 Withdrawal criteria

Patients can be withdrawn from the trial if:

- They withdraw their consent at any point during the study **for any reason**. This can happen at any time after consent and during follow up. In such an event no additional data will be collected from the patient and there will be no follow up. The study doctor will ascertain whether the patient wishes the withdrawal of consent to apply retrospectively to the withdrawal (i.e. can we use data already collected?). The outcome of any and all discussions regarding the withdrawal of consent will be documented in the medical notes and case report form.
- A patient's condition deteriorates due to heart failure or another pathology to the extent that they are expected to die within the next 24 to 48 hours.
- The study doctors deems the risk of continuation due to serious drug reactions or adverse events is too great to the patient. This will be fully discussed with the patient and the content and outcome of all discussions will be documented in the medical notes and CRF.
  - Worsening symptoms of heart failure\*
  - Hyponatraemia (<135 mmol/L)
    - Asymptomatic\*
      - Severe (<130 mmol/L)\*

    - Symptomatic (confusion, drowsiness, nausea or vomiting)\*\*
  - Hypotension
    - Asymptomatic\*
    - Symptomatic with no sequelae\*
    - Symptomatic with significant sequelae i.e. fall due to postural hypotension\*\*
  - o Hyperchloraemia
    - Mild 107 110 mmol/L\*
    - Severe >110mmol/L\*\*
  - Worsening renal function
    - >30% increase in serum creatinine from admission. \*
    - >50% increase in serum creatinine from admission.\*
    - >100% increase in serum creatinine from admission.\*\*
  - Side effects of acetazolamide: haemorrhage, ataxia, depression, diarrhoea, dizziness, fatigue, flushing, irritability, headache, loss of appetite, nausea, vomiting, taste disturbance, paraesthesia,
    - Tolerable to the patient.\*
    - Intolerable to the patient.\*\*

\* - Clinically relevant safety endpoint that would not automatically lead to the discontinuation of the study drug. Withdrawal would be at patient's request or the study doctor's discretion if the risk of continuation was deemed too high.

\*\* - Occurrence would lead to withdrawal from the study if it occurred in the acetazolamide arm

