# 9.2 Operational definitions for (S)AEs

Due to the pilot and exploratory nature of this study **all** adverse events and adverse reactions will be recorded. All serious adverse events serious adverse reactions, and suspected unexpected serious adverse reactions will be reported.. This will enable collection on safety data for the use of ACZ concurrently with high dose loop diuretics as well as data on the tolerability of treatment for a future trial.

	Asymptomatic hypotension (systolic blood pressure (SBP) <90 mmHg)
	Symptomatic hypotension (SBP <90 mmHg and symptoms of: dizziness or presyncope)
	Asymptomatic hyponatraemia (serum sodium concentrations <130 mmol/L)
Adverse Events	Symptomatic hyponatraemia (serum sodium concentrations <130 mmol/L and symptoms of fatigue, nausea, vomiting, or headache not promoting further treatment or investigation)†
	Flare of gout requiring oral treatment and analgesia
	Decrease in estimated glomerular filtration rate >50% of baseline value
	† Treatment of headache with analgesia not included in this definition however treatment of nausea or vomiting with antiemetic is.
	Symptomatic hypotension with sequelae (SBP <90 mmHg and symptoms of: dizziness or presyncope and fall or injury as a direct result)
	Symptomatic hyponatraemia with sequelae (serum sodium concentrations <130 mmol/L and symptoms of fatigue, nausea, vomiting, headache which prompt further treatment or investigation,† or confusion or seizure deemed secondary to hyponatraemia).
	Decrease in eGFR >100% of baseline value or serum creatinine >221µmol/L
	Deterioration in condition during trial defined as:
Serious Adverse Events	
 
Deemed to need escalating doses of loop diuretic or the addition of a second diuretic agent such as thiazide diuretic.
 
Deemed to need inotropic support
 
New diagnosis of infection
 
New diagnosis of another concurrent illness that will prolong hospital stay
 
Transition to end-of-life care
 
Death
 

	Overdose of ACZ or furosemide infusion defined as 1) >500mg given per day of ACZ or 2) >240mg IV furosemide per day.
Adverse Reactions	Metabolic acidosis bicarbonate <23 mmol/L
	Hyperchloraemia 107-110 mmol/L

	Teaching Hospi	tals
	Any of the following possible side effects of acetazolamide that are NHS tolerable to the patient: haemorrhage, ataxia, depression, diarrhoea,	Trust

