# 10.3.3 Secondary outcome analysis

Secondary outcomes are exploratory and none are powered for statistical significance. Secondary outcomes that are measured as continuous variables (difference in daily urine output; difference in weight from baseline to day 4; difference in change in serum sodium potassium, bicarbonate, urea, creatinine, and estimated glomerular filtration rate between baseline and day 4; urinary electrolyte concentrations at day 2 and day 4; inferior vena cava diameter; change in breathlessness score (Likert scale); time to clinical euvolaemia; and length of stay) will be assessed using independent samples t-test, and unadjusted linear regression (with treatment assignment as the independent variable), and linear regression adjusted for daily salt intake and median number of hours of furosemide per day.

Secondary outcomes that are measured as categorical variables (incidence of hyponatraemia, hypochloraemia, hypokalaemia, metabolic alkalosis (serum bicarbonate concentrations >29 mmol/L) or metabolic alkalosis (serum bicarbonate concentrations <23 mmol/L); clinical assessment of congestion; proportion of patients with IVC diameter >2cm; proportion of patients with JVD ratio <4; rate of adverse and serious adverse events; rate of drop-out after randomisation will be assessed using chi-squared tests, un-adjusted logistic regression (with treatment assignment as the independent variable), and logistic regression adjusted for daily salt intake and median number of hours of furosemide per day.

Survival analysis (time to cause specific hospitalisation and time to cause specific mortality) will be conducted with a time-to-first event analysis using Kaplan-Meier and logrank tests, un-adjusted Cox proportional-hazard outcome models.

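### High serum chloride, a listed safety event, is not identifiably compared between arms, because the two-arm electrolyte outcome counts chloride only when it is low

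*Protocol*

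**What the plan says.** **Co-primary.** Section 3.4 defines the chloride endpoint as "Serum chloride day 4 – serum chloride day 1", a signed change with no upper limit. Section 10.3.2 compares it between arms by t test. The primary hypothesis is that acetazolamide works by "reducing the amount by which serum chloride concentrations fall during diuresis". Section 1 adds that "An additional benefit of acetazolamide may be increased renal chloride reabsorption and thus increased serum levels during diuresis".

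**Two-arm electrolyte outcome.** Section 3.5 item 3 lists the "incidence of electrolyte abnormalities; hyponatraemia (<135 mmol/L), hypochloraemia (<96 mmol/L), hypokalaemia (<3.5 mmol/L), high (>30 mmol/L) or low (<22 mmol/L) serum bicarbonate". The matching list of categorical tests in Section 10.3.3 opens with "incidence of hyponatraemia, hypochloraemia, hypokalaemia, metabolic alkalosis" and goes on to low bicarbonate. Neither list contains high chloride.

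**High chloride as a safety matter.** Section 9.2 lists "Hyperchloraemia 107-110 mmol/L" among adverse reactions and severe hyperchloraemia among serious adverse reactions. It is not among the listed adverse events or serious adverse events. Section 7.9 has a mild band of 107-110 mmol/L and a band "Severe >110mmol/L"; the second leads to withdrawal if it occurs in the acetazolamide arm.

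**Who is counted.** Section 3.5 item 11 gives the rate of adverse reactions for the treatment arm. Item 12 gives adverse events and serious adverse events for both arms, and Section 10.3.3 tests those overall rates.

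**Entry.** The exclusion is "Serum chloride (severe hyperchloraemia) >110 mmol/L at randomisation", so a patient at 107-110 mmol/L may be randomised. There is no lower chloride limit.

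**The concern.** Acetazolamide is being tested for its ability to hold serum chloride up. High chloride is therefore the abnormality most directly tied to the mechanism, and it is the one chloride abnormality missing from the two-arm list. Bicarbonate, the other acid-base measure, is counted both ways, so the omission looks accidental.

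The pilot is meant to inform a larger trial on chloride homeostasis and tolerability (Section 2). Suppose the mean change is 3.6 mmol/L higher on acetazolamide. That could mean control chloride fell while acetazolamide chloride held steady, or that control held steady while acetazolamide chloride rose, in some patients above range. The outcomes as listed would not tell the reader which of these happened.

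**Working it through.** **1. Where could a high chloride be counted in both arms?**

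| Place | Both arms? | High chloride identifiable? |
|---|---|---|
| 3.4 / 10.3.2 mean change | Yes | No; it is averaged in |
| 3.5 item 3 / 10.3.3 incidence | Yes | No; low chloride only |
| 3.5 item 11, adverse reaction rate | No; treatment arm | Yes, if broken down |
| 3.5 item 12 / 10.3.3, overall adverse event rate | Yes | No; pooled with all other events |
| 3.5 item 15, cause-specific drop-out | Yes | Only above 110 mmol/L, and the withdrawal rule applies to acetazolamide only |

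No row has yes in both columns.

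**2. The plan's own figures.** Section 10.1 takes 0.9 mmol/L per day × 4 days = 3.6 mmol/L and states 14 control and 17 acetazolamide patients. The SD used is not stated. With the admission SD of 3 from Appendix 2, 80% power and two-sided 5%, a t test needs 12 per arm. Inflated for drop-out this is 12/0.9 = 13.3, so 14, and 12/0.8 = 15. That is close to the stated figures and has no bearing on this point; only the 3.6 is carried forward.

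**3. How often might chloride reach 107 mmol/L?** Assumptions:
- Day-1 chloride is normal with SD 3. The mean of 100 is the Appendix 2 median for patients with normal admission chloride. A mean of 98 is an assumed lower value, because hypochloraemic patients may also enter.
- Day-4 chloride is day-1 chloride plus a shift, with or without within-patient noise of SD 2 (assumed). The day-4 SD is then 3 or √(9 + 4) = 3.61.
- P(≥107) = 1 − Φ((107 − mean − shift)/SD). Cutting day-1 values at 110 changes each result by less than 0.1 percentage point.

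| Day-1 mean | Shift | No noise | Noise SD 2 |
|---|---|---|---|
| 100 | 0 | z = 2.33, 1.0% | z = 1.94, 2.6% |
| 100 | +3.6 | z = 1.13, 12.8% | z = 0.94, 17.3% |
| 98 | 0 | z = 3.00, 0.1% | z = 2.50, 0.6% |
| 98 | +3.6 | z = 1.80, 3.6% | z = 1.50, 6.7% |

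A net rise of 3.6 therefore gives about 4-17%, against about 3% or less with no change. If the change added as much variance as baseline (day-4 SD 4.24, mean 100), the figures would be 21% and 5%.

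**4. The same mean difference from prevention alone.** If control falls by 3.6 and acetazolamide is flat, the acetazolamide arm sits on the zero-shift rows (0.1-2.6%) and control is near zero (at most 0.2%). The difference in means is again 3.6, with no material excess of high chloride.

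**5. Numbers of patients.** With 40 recruited 1:1 and 20% drop-out, 20 × 0.8 = 16 acetazolamide patients are analysed. The range 3.6-17.3% is then 0.6 to 2.8 patients. With 20 analysed per arm, power to separate 1% from 13% is about 31%. The count can only be descriptive.

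**The case against.** **High chloride would still be recorded.** Section 9.2 records all adverse events and reactions. Section 9.3 records any clinically significant abnormal laboratory value as an event or reaction. Section 9.5 starts the reaction reporting period regardless of allocation. This stands in part, since the data will exist. But Section 9.1 defines an adverse reaction as a response to the investigational product, and Section 3.5 item 11 reports the rate for the treatment arm. A control-arm value logged as an adverse event enters a pooled rate in which it cannot be seen.

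**Drop-out is compared.** This is partial cover only. The rule applies above 110 mmol/L and in one arm. A patient withdrawn under it before day 4 may also have no co-primary value, and Section 10.7 rules out imputation.

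**This belongs in the analysis plan.** Table layouts do. But the protocol itself fixes the outcome list and the treatment-arm restriction, so the gap is in the protocol.

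**The effect may not occur.** This is fair. The hypothesis is a smaller fall, and under that alone there is no material excess. The secondary outcomes are exploratory and the numbers small.

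**Stronger readings.** A reader might infer that the co-primary scores every rise as benefit, or that harm would be counted as benefit. The documents do not support either. No success rule is written, the null hypothesis is no effect, testing is two-sided, and the stated direction is a smaller fall. Section 7.9 calls 107-110 mmol/L mild and does not make it an automatic reason to stop the study drug.

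**Conclusion.** The point holds as a gap in the outcome list. Followed as written, the trial produces no identifiable between-arm comparison of high chloride, although the protocol treats it as a safety event and measures chloride in both arms. The mean change cannot fill the gap, because the same 3.6 mmol/L difference is compatible with almost no high values or with a visible number of them.

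The size is illustrative: about 4-17% at 107 mmol/L or more after a net rise of 3.6, against about 3% or less with no change. It rests on normality, an SD of 3, a day-1 mean of 98 to 100 and noise SD of 0 to 2. The documents give no SD for the change in chloride. A flat control arm with a net rise on acetazolamide is one possible outcome and is not what the protocol predicts.

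The protocol also contradicts itself on severe hyperchloraemia. Section 7.9 puts it above 110 mmol/L, while the serious adverse reaction row of Section 9.2 prints 107-110 mmol/L, the same band as its non-serious reaction. Any count of severe cases depends on resolving this.

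**What to change.** 1. Reconcile the bands for severe hyperchloraemia in Sections 7.9 and 9.2.
2. Add to Section 3.5 item 3 and Section 10.3.3, in both arms and as a descriptive outcome, the incidence of new chloride of 107 mmol/L or more and of severe hyperchloraemia as reconciled. New means not present at baseline; this is needed because patients may enter at 107-110 mmol/L.
3. Beside the chloride co-primary, report a table by arm of day-1 against day-4 chloride category: below 96, 96-106, and 107 or more, with the top category split at the reconciled severe limit.

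The cost is one line in each of two sections and one table. Urea and electrolytes are already scheduled in both arms on days 1 to 4 (Sections 7.7 and 7.8), so no new samples and no change in sample size are needed.
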